We also propose to combine the use of textured shoe insoles with tsDCS. This combinatorial approach may be a potent strategy for simultaneously optimizing spinal responsiveness to input from both descending and ascending excitatory signals to spinal centers of locomotor control. One anticipated benefit of increasing the excitation of spinal locomotor circuits is a reduction in the executive demand of walking, as measured by prefrontal cortical activation. Our research shows that elderly adults rely heavily on compensatory executive control while walking. This is widely considered to be a risk factor for adverse outcomes including falls.

We propose a parallel groups study design in which 40 older adults who have walking deficits and who demonstrate a compensatory executive locomotor control strategy will be randomized into one of four groups: 1) active tsDCS with smooth insoles (active/smooth); 2) sham tsDCS with smooth insoles (sham/smooth); 3) active tsDCS with textured insoles (active/textured); and 4) sham tsDCS with textured insole (sham/textured). Participants will be blinded to group assignment. While receiving stimulation for up to 30 minutes, participants will engage in walking practice over a standardized obstacle course. Practice-related gains in performance will be quantified by walking speed and other biomechanical metrics. Retention of performance gains will also be assessed at a separate visit 2 days later. tsDCS-induced changes in spinal excitability will be assessed by measuring soleus H-reflex. Executive demand of walking will be assessed as prefrontal cortical activation, measured with functional near infrared spectroscopy (fNIRS). Intervening on age-related impairment of the spinal cord to improve walking function is

a promising but untapped area of research. The proposed intervention techniques are low cost and translatable to real-world settings, which enhances the potential long term impact of this work on the well-being of older adults.

4. Background:

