reflex^{21,22}, increases corticospinal excitability²⁴, and increases motor unit recruitment.⁴¹ We propose to deliver tsDCS using an electrode montage that targets lumbar spinal excitability, and has been validated by modeling of electrical current flow⁴² and by gains in lower extremity motor performance.²⁵ The objective with tsDCS is to bring spinal neurons closer to their discharge threshold. When applied during walking, this increased excitability of spinal neurons contributes to a physiological environment that is more responsive to task-specific activation by descending/motor and afferent/sensory pathways.²² The proposed study is designed to provide evidence of short term effects of tsDCS on task practice, which can be translated to longer rehabilitation interventions in the future.

5. Specific Aims:

Specific Aim 1: Acquire preliminary data to assess whether active tsDCS and/or textured shoe insoles improve practice-related gains in performance and retention for a complex obstacle walking task.

Hypothesis 1a: Within-session, effect sizes will support the following group differences for improved walking speed and reduced prefrontal activity after the practice period:
[active/textured] > [active/smooth = sham/textured] > [sham/smooth]

Hypothesis 1b: At the 2-day retention test, effect sizes will support the same findings described for Hyp 1a.

Specific Aim 2: Establish evidence of increased spinal excitability following tsDCS.

Hypothesis 2: Spinal excitability post-stimulation (measured by H-reflex) will be significantly elevated above pre-stimulation baseline for active tsDCS but not sham tsDCS.

6. Research Plan:

Study Overview

All study procedures will be conducted at the Brain Rehabilitation Research Center within the Malcom Randall VA Medical Center. Up to forty older men and women will be enrolled in the intervention component of this study. A larger number will be enrolled for onsite screening, because some will fail the screening tests and not proceed to the study intervention.

Participants will undergo the following sequence of events:

- *Telephone Screening:* Volunteers will be screened by telephone to determine if they meet basic enrollment criteria including age and general health status.

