- *Informed Consent and Onsite Screening Visit:* Volunteers who pass the phone screen will be invited to participate in on-site screening. Informed consent will be obtained. Mobility function, cognitive screening, and somatosensory screening will be conducted. This visit will last approximately 3 hours.
- *Study Intervention Visit(s):* Qualifying participants will be invited to participate in the full study. They will attend either one or two intervention sessions (randomly determined to study dosage effects) in which they will practice a “locomotor learning” task comprised of a 10m walking course with obstacles and transitions between hard and soft floor surfaces. During this task they will receive either active or sham transcutaneous spinal direct current stimulation. They will also wear either smooth or textured shoe insoles. Biomechanical and neural control of walking will be assessed with various non-invasive

modalities. Participants will also undergo H-reflex assessment. This visit will last approximately 3 hours.

- *Follow up Visit:* 2 days following the study intervention visit, participants will return to perform the “locomotor learning” task again so that we can assess retention of learning. This visit will last approximately 2 hours.

Telephone Screening

Participants will be screened by telephone to determine if they meet the following criteria:

Inclusion criteria

- Age 65 years or older
- Willingness to be randomized to either intervention and to participate in all aspects of study assessment and intervention

Exclusion criteria

- Diagnosed neurological disorder or injury of the central nervous system, or observation of symptoms consistent with such a condition (spinal cord injury, Alzheimer’s, Parkinson’s, stroke, etc.)
- Contraindications to non-invasive spinal stimulation including any prior spinal surgical procedure
- Chronic lower back pain
- Obesity, defined as Body Mass Index exceeding 30. This is due to the potential influence of body fat on the amplitude of electrical current flow to the spinal cord.
- Use of medications affecting the central nervous system including, but not limited to, benzodiazepines, anti-cholinergic medication and GABAergic medication.
- severe arthritis, such as awaiting joint replacement
- current cardiovascular, lung or renal disease; diabetes; terminal illness
- myocardial infarction or major heart surgery in the previous year

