During the walking practice protocol, participants will receive either active or sham transcutaneous spinal direct current stimulation (tsDCS) and will wear either smooth or textures shoes insoles. Specifically, participants will be randomized to one of four groups: active tsDCS with smooth insoles (*active/smooth group*); 2) sham tsDCS with smooth insoles (*sham/smooth group*); 3) active tsDCS with textured insoles (*active/textured group*); and 4) sham tsDCS with textured insole (*sham/textured group*). More detail about tsDCS and insoles are given below.

Transcutaneous spinal direct current stimulation (tsDCS) during walking practice protocol
tsDCS will be delivered to the posterior lumbar region of the spinal cord during walking using a commercially available direct current stimulation unit (Soterix Medical Inc). Each tsDCS electrode is comprised of a carbon rubber electrode encased in a saline-soaked sponge. The anode electrode will be placed on the skin over the 11th and 12th thoracic vertebrae, and the cathode electrode will be placed over the umbilicus. This electrode configuration has been shown to appropriately target the lumbosacral spinal cord, as validated by modeling of electrical current flow⁴² and by gains in lower extremity motor performance.²⁵ A standard dosage of up to 30 continuous minutes of 2.5 mA stimulus will be used. This dosage (or similar) has been used in numerous prior studies and has been shown to be well-tolerated and to produce measurable changes in reflex activity and/or lower extremity motor performance.^{23-25,38,39,43,44} An identical electrode arrangement will be used for the sham condition, except the stimulation will be delivered in a brief ramp-like manner for just a few seconds at the beginning and end of the stimulation period. This sham approach is widely used in the field of direct current stimulation, and has been reported to be indistinguishable from active stimulation.^{39,45} This is because participants quickly habituate to the sensation of active stimulation.

Textured Shoe Insoles during walking practice protocol

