Each participant will be tested using smooth insoles and textured insoles. Both insole types will be created with 3D printing technology (SolidWorks software and Makerbot Replicator 2 printer). The insole material is a thin flexible plastic called Acrylonitrile Butadiene Styrene. This base material is extremely thin (about 1.5 millimeters) and does not substantially alter the fit or feel of the shoe. The smooth insole will consist of only this base material. The textured insole will use the same base material, but with firm raised cylindrical bumps (approximately 2.5mm height and 2.0mm diameter) spaced in a grid pattern. The grid of bumps will be located under the big toe, the head of the first metatarsal, the heads of 2nd-5th metatarsals, and the heel. On average, the typical insole will have 30-50 bumps depending on the size of the individual's foot. All insoles will be custom-sized to fit the participants' feet. All participants will wear socks (new out of package) and appropriately sized sandals (sanitized between study visits) that we provide. The sandals will be "walking sandals" with adjustable padded straps across the forefoot and heel.

Dual Task Walking Protocol

We will also ask participants to perform dual-task walking tests with a verbal phonemic fluency task and/or with a serial-7 subtraction task. Dual-task cost will be quantified as decrements in performance on either walking (e.g., slowing of walking speed) or cognitive task (e.g., fewer correct responses). Participant responses will be captured with a voice recorder and quantified as rate of word generation (after accounting for incorrect or repeated words). Participants will be instructed to focus equally on both the walking task and the cognitive task, in order to ensure divided attention.

Assessments of walking performance and neural control

Various assessments of walking performance and neural control will be made during the walking practice protocol, or during separate periods of walking, or while at rest.

Biomechanics and movement data

Performance on walking tests will be assessed using motion analysis instrumentation such as force plates, motion capture camera, and/or an electronic walkway. When motion capture cameras are used, we will tape small reflective markers to the participant's body which are visible to the camera and allow offline calculation of joint movements.

fNIRS prefrontal activation

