Participants may be asked to wear sensors on their fingers that measure skin conductivity, which is a measure of sympathetic nervous system arousal. Adhesive electrodes are placed on the index and ring fingers. We will use a commercially available data acquisition unit (Flexcomp Infiniti by Thought Technologies Inc).

Video, photos, and voice recordings

During this study, videos and/or photos may be taken during to document the functional abilities of participants, and for possible use in research presentations or education. We may also use voice recordings to capture performance on cognitive assessments such as verbal fluency or serial-7 subtraction tests. At the time of consent, participants will choose what their videos/photos/recordings can be used for. We will avoid capturing images of the participants' faces, and will obscure or delete any such images.

Follow Up Visit

Approximately 2 days after the intervention visit, participants will return to the lab and perform several more walking trials on the same course that was used for practice, so that we can evaluate retention of walking performance.

The dual-task walking assessment will also be repeated.

Possible Discomforts and Risks:

As with all physical activity, there is a risk of falling while we test or train walking ability. Falls can lead to injuries ranging from minor to serious. When participants are asked to walk on a treadmill (e.g., during the H-reflex test described above), they will wear a safety harness so that they cannot fall off the treadmill. The harness will catch the participant, but might still cause injury (scrapes or bruises) if there is forceful contact with the straps. It is also possible that participants could experience musculoskeletal injury such as an ankle sprain. It is possible that the participant may experience fatigue, soreness, and discomfort due to physical activity associated with this study. These are unlikely to be worse than what he/she would experience due to increased physical activity outside of our study. These are normal responses to exercise and most discomfort would generally disappear within a matter of days. In general, walking exercise is strongly recommended for all adults, including elderly adults with medical conditions.

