Transcutaneous spinal direct current stimulation is considered safe but some people might experience some side effects. The most common side effects are itching and tingling or mild discomfort at the area of stimulation. Whenever an electrical stimulation is applied to the body, it could possibly have unexpected consequences. tsDCS will be applied and operated by research personnel listed in myIRB (with all required training in human subjects research) who have been thoroughly trained in the use and safety of tsDCS by the investigative team.

Furthermore, we will carefully document any potential adverse reactions. We will closely monitor any potential discomfort, irritation, redness, muscle spasms, altered sensation, or changes in autonomic function due to tsDCS with questionnaires conducted at each session and also with a follow-up phone call.

Textured insoles are generally safe, although we will impose exclusion criteria related to foot health including prior history of foot ulcer, present signs of broken skin or blisters, and/or structural deformity causing major pressure points on the sole of the foot. If necessary, the textured insoles can be trimmed or particular regions can be sanded down to avoid irritating sensitive areas on the sole of the foot. The participants' feet will be visually examined prior to and following the assessment, and the participant will be interviewed about any potential discomfort. Any noteworthy issues will be recorded.

fNIRS is considered safe. The infrared light used in assessment is not known to cause any harm or to alter the brain in any way. The sensors are secured to the participant's head using adhesive tape, which may cause minor skin irritation in some people, particularly those who are sensitive/allergic to adhesives. We will check with participants about any known sensitivities to adhesives.

There is a risk that participants may find cognitive and functional tests challenging or uncomfortable if they have difficulty succeeding with the tasks. Participants may skip any question that they do not wish to respond to.

8. Possible Benefits:

There is no direct benefit to the participant.

9. Conflict of Interest:

None.

Data and Safety Monitoring Plan

Adverse Event Reporting

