
fNIRS Safety: fNIRS poses no safety risk. Infrared light from the fNIRS device is not harmful and elicits no sensation. Sensors may be secured to the skin using adhesive tape, which could lead to mild skin irritation in those who are sensitive to adhesives. If a person indicates or displays such a sensitivity, we will avoid using adhesive tape and instead use elastic fabric or straps to secure the sensors.

Questionnaire administration: Questionnaire data are collected in secure spaces where the interview cannot be overheard. Participants will be informed that they are not required to answer questions that they do not wish to answer.

Statistical Analysis Plan: Effect sizes for between-group differences will be calculated for *improved* walking speed after the practice period. For Hypothesis 1b, an analogous comparison

will be made for the 2-day retention test. We do not claim that this study is powered to conduct statistically significant tests of group differences, although we will examine our data for evidence of directional effects:

[active/textured] > [active/smooth = sham/textured] > [sham/smooth].

Rather, our goal is to calculate effect sizes and variance of response in order to provide data needed for powering a future full scale trial. This study will also provide information on the feasibility of our protocol including safety and recruitment.

1. Fielding, R.A., W.J. Rejeski, S. Blair, T. Church, M.A. Espeland, T.M. Gill, J.M. Guralnik, F.C. Hsu, J. Katula, A.C. King, S.B. Kritchevsky, M.M. McDermott, M.E. Miller, S. Nayfield, A.B. Newman, J.D. Williamson, D. Bonds, S. Romashkan, E. Hadley, M. Pahor, and L.R. Group, *The Lifestyle Interventions and Independence for Elders Study: design and methods*. Journals of Gerontology. Series A, Biological Sciences and Medical Sciences, 2011. **66**(11): p. 1226-37.
2. Shumway-Cook, A., A. Patla, A. Stewart, L. Ferrucci, M.A. Ciol, and J.M. Guralnik, *Environmental components of mobility disability in community-living older persons*. J Am Geriatr Soc, 2003. **51**(3): p. 393-8.
3. Shumway-Cook, A., A.E. Patla, A. Stewart, L. Ferrucci, M.A. Ciol, and J.M. Guralnik, *Environmental demands associated with community mobility in older adults with and without mobility disabilities*. Phys Ther, 2002. **82**(7): p. 670-81.

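### The insole section has every participant tested in both insole types, which conflicts with the four parallel groups, one insole type each, behind the Hypothesis 1 effect sizes

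*Combined protocol and SAP*

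**What the plan says.** Most of the plan describes one insole type per person. The Abstract says "We propose a parallel groups study design in which 40 older adults who have walking deficits" are randomized into four groups. The Study Intervention Visit(s) entry in the Study Overview says of participants: "They will also wear either smooth or textured shoe insoles". The Walking practice protocol section repeats that they "will wear either smooth or textures shoes insoles" and lists the four tsDCS/insole combinations. Hypothesis 1a orders those groups as "active/textured] > [active/smooth = sham/textured] > [sham/smooth", and Hypothesis 1b carries the same order to the 2-day retention test. The Statistical Analysis Plan calculates between-group effect sizes for improvement in walking speed, makes no claim of power, and states that "our goal is to calculate effect sizes and variance of response in order to provide data needed for powering a future full scale trial".

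The section Textured Shoe Insoles during walking practice protocol begins differently: "Each participant will be tested using smooth insoles and textured insoles". The rest of that section covers material, bump layout, sizing and footwear. It does not return to who wears what, or when.

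Two other places bear on insoles. Under Follow Up Visit, participants return to "perform several more walking trials on the same course that was used for practice", with no mention of which insole is worn. Under Possible Discomforts and Risks there are foot-health exclusions, trimming or sanding of insoles, a check in which the participants' "feet will be visually examined prior to and following the assessment", and an interview about discomfort.

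**The concern.** Insole type is half of every group label in Hypothesis 1. A rule that puts each person in both types, placed under a heading about the practice protocol, makes insole a within-person factor in the period when the groups are meant to differ by insole. Someone running visits from the insole section could give smooth-group participants passes in textured insoles. The sham/smooth group would then no longer be free of texture, and the step from smooth to textured within each tsDCS arm would shrink.

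The pilot's product is the effect sizes and variances meant to power a later trial. A diluted insole contrast would carry straight into that calculation, and a reader of the results could not tell from the protocol what had been worn.

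**Working it through.** The plan gives no sample-size or power figure for this point, so there is nothing to reproduce. The check is mainly textual.

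**1. The statements side by side**

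| Place | Insole types per person |
|---|---|
| Abstract | One, by parallel group |
| Study Overview, intervention visit | One (either/or) |
| Walking practice protocol | One (either/or, four groups) |
| Hypotheses 1a and 1b | One, as part of the group label |
| Statistical Analysis Plan | One, implied by between-group effect sizes |
| Textured Shoe Insoles section | Both, for each participant |

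**2. Can they be reconciled?** The protocol allows some assessments in separate periods of walking, so the sentence could refer to a test outside practice. But its heading places it in the practice protocol, and no section describes a two-insole test, an order, a washout or a paired analysis. Reading it as saying only that both types are used somewhere in the study does not fit a statement about each participant.

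**3. What follows if it is carried out depends on timing, which is not given**

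- Before or during practice: Hypotheses 1a and 1b are both affected.
- After the post-practice measurement but before the 2-day test: only Hypothesis 1b is affected.
- After the last retention pass: neither is affected.

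**4. Illustrative size.** Assume that benefit is proportional to the share of passes walked in textured insoles, and that each person walks a share f in the non-assigned type. The textured groups then have a textured share of 1 − f and the smooth groups f. The contrast is (1 − f) − f = 1 − 2f of its true size.

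| f | Share of effect left | Example, true d = 0.5 |
|---|---|---|
| 5% (1 pass of 20) | 0.90 | 0.45 |
| 10% | 0.80 | 0.40 |
| 25% | 0.50 | 0.25 |
| 50% | 0 | 0 |

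At f = 50% the two insole groups within a tsDCS arm have the same exposure. Only the tsDCS contrast remains, and the hypothesized order cannot appear. Neither f nor d is in the documents.

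**5. Precision, for scale.** No allocation ratio is stated; equal allocation gives 40/4 = 10 per group. For a pairwise effect size, SE = sqrt(2/n + d²/(4n)). With n = 10:

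- d = 0: sqrt(0.2) = 0.447, 95% half-width 1.96 × 0.447 = 0.88.
- d = 0.5: sqrt(0.2 + 0.00625) = 0.454, half-width 0.89.
- d = 0.8: sqrt(0.2 + 0.016) = 0.465, half-width 0.91.

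A shift from 0.50 to 0.45 or 0.40 is small beside 0.89. It is still a systematic error, whereas the half-width describes random error.

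The two designs also give different precision for an insole main effect. With 20 v 20 in parallel, SE = sqrt(2/20) = 0.316. With all 40 measured in both types and within-person correlation ρ, SE = sqrt(2(1 − ρ)/40), which is 0.187, 0.158 or 0.122 at ρ = 0.3, 0.5 or 0.7. The correlation is an assumption.

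**The case against.** The strongest reply is that one introductory sentence, in a section mostly about how insoles are made, is outweighed by the Abstract, the Study Overview, the randomization text, the hypotheses and the Statistical Analysis Plan. Staff would very likely follow the group assignment, and the analysis is stated as between-group. That stands as to probable intent and lowers the severity. It does not remove the conflict, because the sentence sits under the practice heading and gives a rule that is wrong for this design.

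It is also fair that every figure for the bias rests on assumed inputs, that a stray pass or two would matter little beside the sampling error, and that no contamination follows if the two-insole test comes after retention. All of this stands.

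A reader might infer more than the documents support:

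- **That the trial is really a crossover with the wrong analysis.** No section proposes a paired analysis or an order of conditions, and the stated analysis fits the parallel design.
- **That a paired effect size will mislead the future trial.** This would need an analysis that the plan does not propose.
- **That the smooth groups will certainly have worn texture before retention.** The text gives no timing.
- **That skin reactions could not be traced to an insole type.** The discomfort interview and the recording of noteworthy issues may help with this, as well as the foot check.

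**Conclusion.** Wrong as written, at low-to-moderate severity. The insole section's opening sentence contradicts the parallel four-group design and the between-group effect sizes. It is probably leftover wording. If acted on before or during practice, or before the 2-day test, it would bias the Hypothesis 1 insole contrasts toward zero, provided that textured insoles help and that exposure during practice carries into what is measured. The size of the bias cannot be derived from the documents; the proportions left (0.90 down to 0) show only how it would vary with the share of passes in the other type. No sample size or power statement is wrong, because the plan makes none.

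The missing statement of which insole is worn at baseline and at the 2-day test is a separate, secondary omission.

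**What to change.** Replace the opening sentence of the insole section with: *Each participant will wear only the insole type of the assigned group (smooth or textured) during the walking practice protocol.* For the subset that practises twice, this should cover both sessions.

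If a two-insole comparison is wanted, place it after the last retention pass and report it separately from the Hypothesis 1 effect sizes.

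As a secondary clarification, state which insole is worn at baseline and at the 2-day test, with the same rule for all groups. This is partly a choice of what to estimate. Raw retention speed in the assigned insole includes any immediate insole effect, while a gain from a baseline in the same insole cancels an additive one. The protocol should say which score is meant.

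If any participant has already walked in both types, report the number of passes in each type by group.

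The cost is one reworded sentence, one added sentence and no extra participants. An optional two-insole comparison adds a few passes at the end of the follow-up visit.

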Prefrontal brain activity may be measured with fNIRS during walking and cognitive assessments. fNIRS is a safe non-invasive technology for indirectly assessing cortical activation based on changes in blood flow and oxygenation. Sensors are placed on the forehead, and produce infrared light that is able to pass through the skull and is absorbed or reflected by blood and other tissues in the head. Infrared light is considered safe and there is no sensation association with this procedure. Calculations made from the relative amount of light absorption/reflection provide an estimate of the metabolic activity level of underlying cortical tissue. We will use a commercially available fNIRS monitor (Octamon by Artinis Medical Systems).

Muscle activity with surface electromyography (EMG)

EMG is a non-invasive approach to measuring the timing and amplitude of neuromuscular activity by placing recording sensors over the muscles. We may record EMG during walking assessments from up to 8 muscles per leg. Adhesives will be used to secure the electrodes to the legs. Prior to electrode placement, the recording site will be shaved and cleaned to ensure good quality contact.

H-reflex of the soleus muscle to assess spinal excitability

H-reflex testing involves delivering an electrical stimulus to the peripheral nerve and measuring the resultant muscle activity using surface electromyography. H-reflex assessment of the soleus muscle may be conducted immediately preceding tsDCS, as well as immediately post-tsDCS and at 30 minutes post-tsDCS. H-reflex may also be recorded while the participant rests in a semi-reclined positioned with the foot supported in slight ankle dorsiflexion (10 degrees) and the knee in 30 degrees of flexion. H-reflex may also be recorded while the participant is walking on a treadmill or overground. Stimulation will be delivered via a cathode placed in the popliteal fossa and an anode placed above the patella. Electromyography (EMG) will be recorded from the soleus with bipolar surface electrodes place 3 cm apart. Electrode placement will be along the mid-dorsal line of the leg, 4cm below where the gastrocnemius joins the Achilles tendon.

Sympathetic nervous system activity measured by skin conductance

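### Hypothesis 2, the only hypothesis worded as a significance claim, rests on an H-reflex that is optional, has no deciding time point or condition, and has no analysis in the SAP

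*Combined protocol and SAP*

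**What the plan says.** Specific Aims, Hypothesis 2: "Spinal excitability post-stimulation (measured by H-reflex) will be significantly elevated above pre-stimulation baseline for active tsDCS but not sham tsDCS". The other two hypotheses are worded as estimation. Hypothesis 1a: "Within-session, effect sizes will support the following group differences for improved walking speed and reduced prefrontal activity after the practice period". Hypothesis 1b: "At the 2-day retention test, effect sizes will support the same findings described for Hyp 1a".

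On whether the H-reflex is recorded, the documents disagree. The Study Overview, under the intervention visit, says "Participants will also undergo H-reflex assessment", and the Abstract also presents soleus H-reflex as the way excitability will be assessed. The methods section on the soleus H-reflex says instead "H-reflex assessment of the soleus muscle may be conducted immediately preceding tsDCS, as well as immediately post-tsDCS and at 30 minutes post-tsDCS".

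The same section leaves the recording condition open. For rest: "H-reflex may also be recorded while the participant rests in a semi-reclined positioned with the foot supported in slight ankle dorsiflexion". For walking: "H-reflex may also be recorded while the participant is walking on a treadmill or overground". No time point, condition or H-reflex metric is singled out. A random subset of up to 20 participants does the practice protocol twice, and no session is named for the H-reflex comparison.

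The Statistical Analysis Plan covers between-group effect sizes for walking speed after practice and at the 2-day test. It does not mention Hypothesis 2 or the H-reflex, and gives no test, alpha or multiplicity rule. Its statement about limited power concerns group differences.

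**The concern.** Aim 2 is the mechanistic half of the study, and one measure carries it. Followed as written, the methods section lets that measure be skipped, or lets the deciding version be chosen after the data are seen. A rise at either post time, at rest or during walking, could be reported as supporting Hypothesis 2.

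The criterion has a second weakness. A significant change in the active arm without one in the sham arm is a pair of within-arm statements, not a test of active against sham.

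What is at stake is the reliability of a mechanism claim that would help justify a full-scale trial. The walking-speed estimates of Aim 1 are not affected.

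**Working it through.** The documents give no alpha, sidedness, effect size or power for the H-reflex, so there is no stated figure to reproduce.

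**Inputs**
- Post-stimulation times: 2 (soleus H-reflex section).
- Conditions: up to 3 (rest, treadmill, overground; same section). Treadmill and overground may be alternatives, which would leave 2.
- Looks k: 2 if only the two times count; 2 × 2 = 4; at most 2 × 3 = 6.
- Participants: up to 40 in four groups. Pooling over insoles gives 40 / 2 = 20 active and 20 sham if allocation is equal (assumption; no ratio is stated).
- Assumptions: two-sided 5% per look, so 2.5% in the upward direction; a common correlation between looks, varied from 0 to 0.9; no true change.

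**Step 1. Chance of at least one significant look in the active arm.** For independent looks the formula is 1 − (1 − a)^k.
- Rises only, a = 0.025: k = 2, 1 − 0.975² = 4.9%; k = 4, 1 − 0.975⁴ = 9.6%; k = 6, 1 − 0.975⁶ = 14.1%.
- Either direction, a = 0.05: k = 2, 1 − 0.95² = 9.8%; k = 4, 1 − 0.95⁴ = 18.5%; k = 6, 1 − 0.95⁶ = 26.5%.

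Correlated looks were simulated as one-sample t-tests on change scores (n = 20, 40,000 runs):

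| Looks | Counted | Nominal | Corr. 0 (formula) | 0.5 | 0.8 | 0.9 |
|---|---|---|---|---|---|---|
| 2 | rises | 2.5% | 4.9% | 4.5% | 4.0% | 3.4% |
| 4 | rises | 2.5% | 9.6% | 8.1% | 5.8% | 4.8% |
| 6 | rises | 2.5% | 14.1% | 10.7% | 6.9% | 5.4% |
| 2 | either direction | 5% | 9.8% | 9.1% | 7.9% | 7.1% |
| 4 | either direction | 5% | 18.5% | 15.8% | 11.6% | 9.4% |
| 6 | either direction | 5% | 26.5% | 21.4% | 14.2% | 10.9% |

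Hypothesis 2 predicts an elevation, so the rows for rises are the relevant ones.

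**Step 2. Does the sham condition protect?** Requiring a significant rise in active and no significant change in sham at the same look gives, for six looks, 13.6%, 10.3% and 6.6% at correlations 0, 0.5 and 0.8. That is little different from the active arm alone.

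**Step 3. The criterion with a single look.** Suppose both arms truly change by the same amount, so that stimulation adds nothing. With within-arm power p, the chance of significance in active and not in sham is p(1 − p). For an assumed standardised change of 0.5 and n = 20, p = 0.564 and 0.564 × 0.436 = 24.6%. Other assumed changes give 18.6% (0.3, p = 0.246) and 16.0% (0.66, p = 0.799). Naming one measure does not remove this problem; comparing the arms does.

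**The case against.** The strongest reply is that this is a pilot whose SAP aims at effect sizes, variance of response and feasibility, with no confirmatory test planned. That stands in part: the inflation is conditional, because no alpha is stated and nothing says that any favourable look would suffice. But the power statement concerns group differences, while Hypothesis 2 claims significance within arms, so the statement does not clearly reach it.

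It is also fair that six looks is a ceiling. The walking sentence may mean one mode per person, and the sentence giving the times is separate from those giving the conditions; nothing says walking recordings are made at both post times. The only count stated directly is two post times.

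A reader might infer a false-positive risk of 26%. The documents do not support that as the plan's error rate: it needs six independent looks at one reflex in the same people, an unstated 5% level, and decreases counted alongside increases.

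A reader might also infer that optional recording makes the data depend on who tolerated the test, and so breaks the randomised comparison. No section links H-reflex recording to tolerance. The same permissive wording is used for fNIRS, EMG and skin conductance, and Hypothesis 2 as worded is not a randomised comparison.

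**Conclusion.** The concern holds in a limited form. The texts conflict on whether Aim 2's only measure is taken at all, no version of it is designated as deciding, and the SAP has no analysis for it. These points need no assumptions.

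The size does need assumptions: a two-sided 5% level per look, an unknown correlation, and freedom to count any favourable look. On that basis the chance of a false rise in the active arm is about 7% to 14% for six looks, the maximum, at correlations of 0.8 down to 0, against 2.5%. Counting either direction, two time points give about 8% to 10% over the same correlations, and six independent looks give an upper bound of about 26%, against 5%. The excess over nominal shrinks as correlation rises but does not vanish at any value examined.

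The consequence is an unreliable mechanistic statement, not a wrong efficacy conclusion. The plan should be changed, since the correction is cheap.

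**What to change.** 1. Reconcile the optional wording in the soleus H-reflex section with the definite wording in the Abstract and Study Overview, so that the H-reflex is recorded before and after stimulation in all randomised participants.
2. Name in advance one condition, one post time, one session and one H-reflex metric as the measure deciding Hypothesis 2. Semi-reclined rest, from before to immediately after stimulation, is one reasonable choice because it is the only condition whose posture is specified. The investigators may prefer another, for instance a walking recording since stimulation is given during walking, provided it is named beforehand.
3. Add to the SAP an analysis of that measure: the active-minus-sham difference in change, with a confidence interval, in place of significance in one arm and not the other.
4. Label all other H-reflex recordings exploratory.

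The cost is a few sentences in the protocol and a short SAP paragraph, plus the effort of recording everyone, which the Study Overview already promises. The downside is that a change seen only at another time or in another condition could not be claimed as confirming Hypothesis 2. If several looks must stay decisive, a Bonferroni split of 5% would require 0.05 / 2 = 0.025 per look for two and 0.05 / 6 = 0.0083 for six, which is demanding at this sample size.
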